4.1.3 Exclusion Criteria

Any of the following would exclude the subject from participation in the study:

- 1. Concurrent enrollment in another clinical study where the subject is receiving an investigational product
- 2. Individuals who are legally institutionalized
- 3. Receipt of any marketed or investigational biologic agent within 4 months or 5 half-lives prior to screening, whichever is longer
- 4. Receipt of any investigational nonbiologic agent within 3 months or 5 half-lives prior to screening, whichever is longer

- 5. Known history of allergy or reaction to any component of the investigational product formulation
- 6. History of anaphylaxis following any biologic therapy
- 7. Current use of regular pain-modifying, anti-depressant, anxiolytic, or hypnotic medication
- 8. History of thrombocytopenia or bleeding disorder or use of anticoagulants such as warfarin, heparin/low molecular weight heparin, thrombin inhibitors (dabigatran and others), or factor Xa inhibitors (rivaroxaban, apixaban, and others)
- 9. Any pathology on abdomen that could potentially interfere with study outcome or interpretation of results
- 10. History of chronic alcohol or drug abuse within 12 months prior to screening, or any condition associated with poor compliance as judged by the investigator
- 11. Pregnant or breastfeeding women
- 12. Any active medical or psychiatric condition or other reason which, in the opinion of the investigator or medical monitor, may compromise the safety of the subject in the study or interfere with evaluation of the investigational product or reduce the subject's ability to participate in the study
- 13. Any clinically relevant abnormal findings in physical examination, ECG, vital signs, hematology, clinical chemistry, or urinalysis during screening, which in the opinion of the investigator or medical monitor may compromise the safety of the subject in the study or interfere with evaluation of the investigational product or reduce the subject's ability to participate in the study
- 14. History of any known immunodeficiency disorder or use of immunosuppressive medication
- 15. History of a clinically significant infection requiring antibiotics or antiviral medication from 30 days prior to screening, up to and including Day 1
- 16. Diagnosis of a helminth parasitic infection within 6 months prior to screening that has not been treated with, or has failed to respond to, standard of care therapy
- 17. History of cancer, except for basal cell carcinoma or in situ carcinoma of the cervix treated with apparent success with curative therapy ≥ 12 months prior to screening or other malignancies treated with apparent success with curative therapy ≥ 5 years prior to screening
- 18. Tuberculosis requiring treatment within the 12 months prior to the screening visit
- 19. Positive hepatitis B surface antigen or hepatitis C virus antibody serology. Subjects with a history of hepatitis B vaccination without history of hepatitis B are allowed to enroll.
- 20. A positive human immunodeficiency virus (HIV) test at screening or subject taking antiretroviral medications, as determined by medical history and/or subject's verbal report
- 21. Evidence of active liver disease, including jaundice or aspartate transaminase (AST), alanine transaminase (ALT), or alkaline phosphatase greater than twice the upper limit of normal (ULN)
- 22. Major surgery within 8 weeks prior to Visit 1, or planned in-patient surgery or hospitalization during the study period

23. Receipt of live attenuated vaccines 30 days prior to screening, up to and including Day 1

4.1.4 Subject Enrollment and Randomization

Study participation begins (ie, a subject is "enrolled") once written informed consent is obtained. Once informed consent is obtained, a subject identification (SID) number will be assigned and the screening evaluations may begin to assess study eligibility (inclusion/exclusion) criteria. The SID number will be used to identify the subject during the screening process and throughout study participation, if applicable.

A master log of all consented subjects will be maintained at the site and will document all screening failures (ie, subjects who are consented but do not meet study eligibility criteria and/or are not randomized), including the reason(s) for screening failure.

If at the screening visit, a subject provides a medical history that is exclusionary but the subject is expected to subsequently become eligible (eg, fails a time-sensitive exclusion criterion), one repeat screening visit will be permitted. Such subjects will receive the same SID number that they were originally assigned.

4.1.5 Withdrawal from the Study

Subjects are at any time free to withdraw from the study (investigational product and assessments), without prejudice to further treatment (withdrawal of consent). Such subjects will always be asked about the reason(s) and the presence of any AEs. If possible, they will be seen and assessed by an investigator. Adverse events will be followed up. If a subject withdraws from further participation in the study, then no further study visits or data collection should take place.

4.1.6 Replacement of Subjects

Subjects who do not receive tralokinumab after being randomized or do not complete the required evaluations through Day 8 will be replaced to maintain the stipulated number of subjects in each cohort (N = 15). Replacement subjects will receive the same treatment assignment as the subject being replaced and every attempt will be made to ensure that they are from the same gender group. Subjects who do not complete the required evaluations beyond Day 8 will not be replaced.

4.1.7 Withdrawal of Informed Consent for Data and Biological Samples

Biological Samples Obtained for the Main Study

Study data are protected by the use of an SID number, which is a number specific to the subject. The investigator is in control of the information that is needed to connect a study sample to a subject. A subject's consent to the use of data does not have a specific expiration date, but the subject may withdraw consent at any time by notifying the investigator. If consent is withdrawn, any samples collected prior to that time may still be given to and used by the sponsor but no new data or samples will be collected unless specifically required to monitor safety of the subject.

4.2 Schedule of Study Procedures

4.2.1 Enrollment/Screening Period

Table 4.2.1-1 shows all procedures to be conducted at the screening visit. Screening evaluations may be conducted over more than one visit; however, the results of all laboratory tests must be available prior to dosing on Day 1.

Whenever vital signs, 12-lead ECGs, and blood draws are scheduled for the same nominal time, the assessments should occur in the following order: 12-lead ECG, vital signs, and then blood draws.

Study Period	Consent/Screening				
Visit Number	V1				
Procedure / Study Day or Week	Day -21 to Day -1				
Written informed consent/assignment of SID number	X				
Verify eligibility criteria	Х				
Demography and medical history	X				
Physical examination, height, and weight	Х				
12-lead ECG	X				
Assessment of AEs/SAEs	Х				
Concomitant medications	X				
Vital signs	Х				
Blood collection for:	X				
Serum chemistry and hematology	Х				
Pregnancy test (serum (3HCG)	Х				
Virology: HBsAG, HCAb; HIV-1, HIV-2	Х				
Urine collection for:	Х				
Urinalysis	X				
Urine drug screen	X				

Table 4.2.1-1 Schedule of Screening Procedures

AE = adverse event; PHCG = beta-human chorionic gonadotrop in; ECG = electrocardiogram; HBsAG = hepatitis B surface antigen; HCAb = hepatitis C antibody; HIV = human inummodeficiency virus; SAE = serious adverse event; SID = subject identification; V = visit.

4.2.2 Treatment Period

Table 4.2.2-1 shows all procedures to be conducted during the treatment period.

Table 4.2.2-2 shows the timing of Day 1 assessments in more detail.

Study Period	Admission to Study Unit	Treatment			
Visit Number	V2	V2			
Procedure / Study Day or Week	Day -1	Day 1			
Verify eligibility criteria	Х	X			
Randomization		X			
Physical examination		X			
Weight		X			
Assessment of AEs/SAEs	Х	X			
Concomitant medications	Х	X			
Vital signs	Х	X			
Blood collection for:		•			
Serum chemistry and hematology	Х				
PK blood sample		X			
IM blood sample		X			
Serum biomarkers		X			
Pregnancy test (serum βHCG)	X				
Urine collection for:					
Urinalysis	Х				
Urine drug screen	Х				
Investigational product administration (300 mg tralokinumab)		X			
Assessment of injection site for:		•			
Fluid leakage and gravimetric analysis					
Pain intensity via VAS		X			
Pruritus via VAS		X			

Table 4.2.2-1 Schedule of Treatment Procedures

Table 4.2.2-1Schedule of Treatment Procedures

Study Period	Admission to Study Unit	Treatment
Visit Number	V2	V2
Procedure / Study Day or Week	Day -1	Day _a 1
Local injection-site reactions ^f		X

AE = adverse event; β HCG = beta-human chorionic gonadotrophin; eCRF = electronic case report form; IM = immunogenicity; PK = pharmacokinetic; SAE = serious adverse event; V = visit; VAS = visual analogue scale.

^a Prior to investigational product administration

- ^b Vital signs (blood pressure, heart rate, respiratory rate, and body temperature) will be assessed prior to, immediately post-injection, and at 10, 30, 60 minutes, and 4 and 8 hours after administration
- ^c Serum samples for PK, immunogenicity, and biomarkers will be collected immediately (within 30 minutes) prior to administration of investigational product
- ^d Assess for fluid leakage immediately post-injection
- ^e Both pain intensity and pruritus at injection site will be assessed by the subject immediately post-injection, once the needle insertion set has been withdrawn (after the second injection in Cohort 1), and at 10, 20, 30, and 60 minutes and then at 2, 4, and 8 hours post-injection for all 4 cohorts. Assessments for pain intensity only at the injection site will be conducted at 1 and 6 minutes during the injection for Cohort 4 only.
- ^f Local injection-site reactions are of specific interest and will be recorded in detail on dedicated and standardized injection site assessment questionnaire (see Appendix 2) at each time point post-injection. These targeted assessment events will not require reporting as AEs on the AE eCRF, unless they meet 1 or more of the following criteria:
 - Fulfils the criteria for an SAE
 - Leads to premature termination of the injection during investigational product administration
 - Requires concomitant medication or other medically important intervention
 - Has an impact on the general condition of the subject as judged by the investigator
- ^g Local injection site reactions (eg, erythema, bleeding, rash, etc) will be assessed by a blinded assessor immediately post-injection (after the second injection in Cohort 1) and at 10, 20, 30, and 60 minutes and then at 2, 4, and 8 hours post-injection for all 4 cohorts

	Prior to IP Admin	During IP Administration		Post IP Administration								
Assessment		1 Min (Cohort 4 only)	6 Min (Cohort 4 only)	Immediately	10 Min (~ 3 min)	20 Min (~ 3 min)	30 Min (~ 3 min)	60 Min (~ 3 min)	2 Hours (~ 10 min)	4 Hours (~ 10 min)	8 Hours (~ 10 min)	
Randomization	X											
Physical examination	X											
Weight	Х											
AEs/SAEs	X	Х	X	X	Х	X	Х	Х	Х	Х	Х	
Concomitant medications	X	Х	X	Х	Х	X	Х	Х	X	X	X	
Vital signs	X			X	Х		Х	Х		Х	X	
Collect blood for:												
РК	X											
IM	X											
Biomarkers	X											
Assess injection site	for:											
Fluid leakage/ gravimetric analysis				Х								
Pain intensity via VAS		Х	X	Х	Х	X	Х	Х	X	X	X	
Pruritus via VAS				X	Х	X	X	X	X	X	X	
Local injection- site reactions ^b				X	X	X	X	X	X	X	X	

Admin = administration; AE = adverse event; IM = immunogenicity; IP = investigational product; Min/min = minute(s); PK = pharmacokinetic; SAE = serious adverse event; VAS = visual analog scale.

^a Injection sites must be assessed in the following order at *all time points* post administration of IP: visual inspection for fluid leakage (immediately post-injection only); VAS scale for pain intensity; VAS scale for pruritus; assessment for local injection-site reactions as outlined in Table 4.2.2-2.

^b Local injection-site reactions to be evaluated by blinded assessor.

4.2.3 Follow-up Period

Table 4.2.3-1 shows all procedures to be conducted during the follow-up period.

Whenever vital signs and blood draws are scheduled for the same nominal time, the assessments should occur in the following order: vital signs, then blood draws. For assessment of injection-site reactions, these should be done in the order specified in the table.

Study Period					Follow-up				
Visit Number	V3	V4	V5	V6	V7	V8	V9	V10	V11
Procedure / Study Day or Week	Day 2	Day 4	Day 6	Day 8	Day 10 (~ 1 d)	Day 15 (~ 1 d)	Day 22 (~ 2 d)	Day 36 (~ 2 d)	Day 57 (~ 2 d)
Physical examination									X
Weight									X
Assessment of AEs/SAEs	Х	X	X	X	X	Х	X	X	X
Concomitant medications	Х	X	X	X	X	Х	X	X	X
Vital signs									X
Blood collection for:									
Serum chemistry and hematology				X		X		X	X
PK blood sample	X ^a	X	X	Х	X	X	X	X	X
IM blood sample									X
Serum biomarkers				X				X	X
Urine collection for:									
Urinalysis									X
Assessment of injection site for:									
Pain intensity via VAS	X ^b	X ^{c, d}							
Pruritus via VAS	X ^b	X ^{c, d}							
Local injection site reactions	X ^b	X ^{c, d}							

Table 4.2.3-1Schedule of Follow-up Procedures

AE = adverse event; d = day; IM = immunogenicity; PK = pharmacokinetic; SAE = serious adverse event; V = visit; VAS = visual analogue scale.

^a PK sample to be collected at 24 hours (~ 30 minutes) relative to administration time on Day 1

^b For each subject, measurements to be taken at 24 hours (Day 2; ~ 1 hour) relative to administration time

^c For each subject, measurements to be taken at 72 hours (~ 1 hour) relative to administration time

^d Symptoms and/or signs at the injection site persisting beyond 72 hours will be followed through resolution

4.3 Description of Study Procedures

4.3.1 Efficacy

Efficacy parameters will not be evaluated in this study.

4.3.2 Medical History and Physical Examination, Electrocardiogram, Weight, and Vital Signs

4.3.2.1 Medical History

Complete medical history will include history and current medical conditions, past or present cardiovascular disorders, respiratory, gastrointestinal, renal, hepatic, neurological, endocrine, lymphatic, hematologic, immunologic, dermatological, psychiatric, genitourinary, drug and surgical history, or any other diseases or disorders.

4.3.2.2 Physical Examination, Height, and Weight

Physical examinations, including weight will be performed by a physician or qualified designee and will include examination of the following: general appearance, head, ears, eyes, nose, throat, neck, skin, cardiovascular system, respiratory system, abdominal system, and nervous system. Each clinically significant abnormal finding will be recorded. Physical examinations will be performed at screening and on Days 1 and 57 as outlined in Table 4.2.1-1, Table 4.2.2-1, and Table 4.2.3-1. Weight will be measured at screening and on Days 1 and 57. Height will be measured at screening only.

4.3.2.3 Vital Signs

Vital signs (blood pressure [BP], heart rate, respiratory rate, and body temperature) will be obtained at screening and on Days -1, 1, and 57 as outlined in Table 4.2.1-1, Table 4.2.2-1, and Table 4.2.3-1.

Day 1, vital signs (BP, heart rate, respiratory rate, and body temperature) will be assessed prior to, immediately after, and at 10, 30, and 60 minutes (~ 3 minutes), and 4 and 8 hours (~ 10 minutes) after administration of investigational product within each cohort. Discharge from site will be determined by the investigator.

All vital sign measurements will be made with the subject in a semi-supine position having rested in this position for at least 5 minutes before each reading.

4.3.2.4 Electrocardiogram

A 12-lead ECG will be obtained after 10 minutes supine rest at screening only as outlined in Table 4.2.1-1. Each lead will be recorded for at least 3-5 beats at a speed of 25 mm/second paper speed and 10 mm/mV amplitude. In addition, a 10-second paper ECG print-out from the 12-lead ECGs will be taken at screening and recorded.

Skin preparation should be thorough and electrode positions should be according to standard 12-lead ECG placement.

In this study, lead V2 will be analyzed and reported as primary. Lead V5 will be analyzed, as backup for the individual subject where analysis in lead V2 is not deemed possible.

The following variables will be reported: heart rate, RR, PR, QRS, and QT and QTc intervals from the primary lead of the digital 12-lead ECG. The Principal Investigator or designated sub-investigator will be responsible for the overall interpretation and determination of the clinical significance of any potential ECG findings.

The investigator may add extra 12-lead ECG safety assessments at any time point during the study if there are any abnormal findings, or if the investigator considers it is required for any other safety reason.

4.3.3 Injection Site Assessments

The injection site(s) will be assessed for pain intensity, pruritus, local injection-site reactions, and fluid leakage. For Cohort 1, assessments will begin after the second 1 mL injection has been administered. The subject will assess injection-site pain intensity and pruritus using a VAS as described in Section 4.3.3.2 and Section 4.3.3.3 and a blinded assessor will assess local injection site reactions as described in Section 4.3.3.4. The investigator or qualified designee will assess investigational product leakage as described in Section 4.3.3.1.

4.3.3.1 Investigational Product Leakage

The investigator or qualified designee will visually examine the injection site for investigational product leakage immediately following the injection, once the needle insertion set has been withdrawn, on Day 1 as outlined in Table 4.2.2-1 and Table 4.2.2-2.

If leakage is present, the injection site will be blotted with pre-weighed absorbent material and the amount of leakage will be quantified and recorded. For subjects in Cohort 1 who will receive 2×1 mL injections of tralokinumab, the overall assessment of fluid leakage from both injection sites combined should be recorded immediately post-injection.

4.3.3.2 Assessment of Injection-site Pain Intensity

Each subject will assess pain intensity at the injection site using a 100 mm VAS immediately post-injection, once the needle insertion set has been withdrawn (after the second injection in Cohort 1), and at 10, 20, 30, and 60 minutes (~ 3 minutes), and then at 2, 4, and 8 hours (~ 10 minutes), and 24 and 72 hours (\pm 1 hour) post-injection for all 4 cohorts. For subjects in Cohort 1 who will receive 2 × 1 mL injections of tralokinumab, the overall assessment of pain intensity from both injection sites combined should be recorded at each time point post-injection. Assessments for injection site pain intensity will also be performed at 1 and 6 minutes during the injection in Cohort 4 given the prolonged injection time (12 minutes) as outlined in Table 4.2.2-1 and Table 4.2.2-2.

The 100 mm VAS for assessment of injection site pain intensity is an ungraduated scale where 0 = "no pain" and 100 = "worst imaginable pain" as described in Appendix 4.

4.3.3.3 Assessment of Injection-site Pruritus

Each subject will assess pruritus at the injection site using a 100 mm VAS immediately post-injection, once the needle insertion set has been withdrawn (after the second injection in Cohort 1), and at 10, 20, 30, and 60 minutes (~ 3 minutes), and then at 2, 4, and 8 hours (~ 10 minutes), 24 hours (\pm 1 hour), and 72 hours (~ 1 hour) post-injection for all 4 cohorts as outlined in Table 4.2.2-1, Table 4.2.2-2, and Table 4.2.3-1. For subjects in Cohort 1 who will receive 2 × 1 mL injections of tralokinumab, the overall assessment of pruritus from both injection sites combined should be recorded at each time point post-injection.

The 100 mm VAS for assessment of injection site pruritus is an ungraduated scale where 0 = "no itch" and 100 = "worst imaginable itch" as described in Appendix 5.

4.3.3.4 Local Injection-site Reactions

Local injection site reactions will be assessed by a blinded assessor (see Section 4.6.2) immediately post-injection, once the needle insertion set has been withdrawn (after the second injection in Cohort 1), and at 10, 20, 30, and 60 minutes (~ 3 minutes), and then at 2, 4, and 8 hours (~ 10 minutes), and 24 and 72 hours (\pm 1 hour) post-injection for all 4 cohorts as outlined in Table 4.2.2-1, Table 4.2.2-2, and Table 4.2.3-1.

The blinded assessor will assess the injection site at each time point post-injection for the presence or absence of signs and/or symptoms of local injection site reaction, including erythema, hematoma or bleeding, local warmth, swelling, and/or rash. In the case of

injection-site rashes, reference should be made to the definitions of rash morphology descriptors found in Appendix 3.

For subjects in Cohort 1 who will receive 2×1 mL injections of tralokinumab, an overall assessment of both injection sites should be recorded at each time point post-injection. Where there are differences in injection site reactions between the two sites for a particular subject, the most severe reaction should always be recorded.

As local injection-site reactions are of specific interest, they will be recorded in detail on a dedicated and standardized injection site assessment questionnaire (Appendix 2) at each time point post-injection. These targeted assessment events will not require reporting as AEs on the AE eCRF, unless they meet 1 or more of the following criteria:

- Fulfils the criteria for an SAE
- Leads to premature termination of the injection during investigational product administration
- Requires concomitant medication or other medically important intervention
- Has an impact on the general condition of the subject as judged by the investigator

Any injection-site reactions that are ongoing beyond 72 hours will be followed up to resolution and the signs/symptoms will be recorded on a local injection-site assessment questionnaire (Appendix 2) at each subsequent visit.

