1.6.2 Secondary Hypotheses

The secondary hypotheses to be tested are:

- 1. Increasing the volume of injection of tralokinumab from 1 mL to 2 mL reduces the tolerability of the injection at a given flow rate (as measured by pain, pruritus, and local injection site reactions)
- 2. Decreasing the flow rate of injection of tralokinumab improves the tolerability of the injection (as measured by pain, pruritus, and local injection site reactions)

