3.1.2 Treatment Regimen

A total of 60 subjects will be randomized in a 1:1:1:1 ratio to 1 of 4 cohorts to receive a single SC dose of tralokinumab as described in Table 3.1.2-1. Randomization will be stratified by gender. At a minimum, 5 males and 5 females will be randomized to each cohort; the additional subjects may be of either sex.

Table 3.1.2-1 Investigational Product Dose and Treatment Regimen

Cohort	Ν	Day 1	
1	15	300 mg tralokinumab as 2×1 mL SC injections, with each injection administered at a flow rate of 6 mL/min	
2	15	300 mg tralokinumab as a 1×2 mL SC injection administered at a flow rate of 12 mL/min	
3	15	300 mg tralokinumab as a 1×2 mL SC injection administered at a flow rate of 2 mL/min	
4	15	300 mg tralokinumab as a 1×2 mL SC injection administered at a flow rate of 0.167 mL/min	

N = number of subjects; SC = subcutaneous.

All injections will be administered into the abdomen via the SC route at the flow rates specified above using a syringe pump and SC insertion set.

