3.2.3 Rationale for Endpoints

Primary Endpoint

The primary endpoint of the study is the PK of tralokinumab. Each subject will receive a single dose of 300 mg tralokinumab by one of 4 administration regimens and 57 days of follow up. Based on prior data, the maximum concentration $_{(Cmax)}$ of tralokinumab usually occurs between 2-9 days with a half-life of approximately 21 days following SC administration. Therefore, the sampling scheme will provide adequate samples for the characterization of $_{Cmax}$ and area under the serum concentration-time curve (AUC) parameters through noncompartmental analysis. The PK parameters associated with a single 2 mL injection of tralokinumab at different flow rates will be compared to those associated with 2×1 mL injections of tralokinumab to determine the feasibility of larger volume delivery and to provide information to aid in the design of the final device.

Secondary Endpoints

Injection site pain will be measured using a 100 mm visual analogue scale (VAS; see Appendix 4). Local injection-site tolerability parameters will also be measured, including injection-site itch and visual assessment of the injection site for reactions such as erythema, rash, etc. As local injection-site reactions are of specific interest, they will be recorded in detail on a dedicated and standardized injection-site questionnaire (Appendix 2) at each time point post-injection. These targeted assessment events will not require reporting as adverse events (AEs) on the AE electronic case report form (eCRF), unless they meet one or more of the following criteria:

- Fulfils the criteria for a serious adverse event (SAE)
- Leads to premature termination of the injection during investigational product administration
- Requires concomitant medication or other medically important intervention
- Has an impact on the general condition of the subject as judged by the investigator

These data will be used to determine the overall tolerability of a single 2 mL injection of tralokinumab at different flow rates to determine the feasibility of this approach compared to 2×1 mL injections and to provide information to aid in the design of the final delivery device.

The degree of fluid leakage from the injection site will be assessed immediately following all injections to determine if the flow rates affect delivery of the 2 mL injection volume.

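### Scoring Cohort 1 reactions as the worse of two sites overstates the per-injection 1 mL rate and weakens the volume comparison in secondary Hypothesis 1

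*Protocol*

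**What the plan says.** Protocol 3.1.2 gives Cohort 1 two 1 mL injections, with "each injection administered at a flow rate of 6 mL/min". Cohorts 2, 3 and 4 receive one 2 mL injection at 12, 2 and 0.167 mL/min.

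For local reactions in Cohort 1, 4.3.3.4 states that "an overall assessment of both injection sites should be recorded at each time point post-injection". If reactions differ "between the two sites for a particular subject, the most severe reaction should always be recorded". Section 4.8.4.4 then summarizes reactions descriptively for each cohort over time.

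For pain in Cohort 1, 4.3.3.2 states that "the overall assessment of pain intensity from both injection sites combined should be recorded at each time point post-injection". For pruritus, 4.3.3.3 states that "the overall assessment of pruritus from both injection sites combined should be recorded at each time point post-injection". Neither section says whether the combined score is the worse site, a sum or an average.

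Two uses of these data are stated:
- Secondary Hypothesis 1 (1.6.2): "Increasing the volume of injection of tralokinumab from 1 mL to 2 mL reduces the tolerability of the injection at a given flow rate".
- Section 3.2.3: the tolerability data are to "determine the feasibility of this approach compared to" 2×1 mL. Section 1.5 frames the study's aim the same way, against the current method of administration.

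**The concern.** Hypothesis 1 asks about one injection of 1 mL against one injection of 2 mL. Cohort 1 is the only cohort with 1 mL injections, but what is recorded for it describes a pair of injections. Each Cohort 1 subject has two chances of being recorded with a reaction, and each subject in Cohorts 2-4 has one. The hypothesis expects the 2 mL injection to be worse. A rule that pushes the 1 mL figure up therefore works against seeing that.

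The issue is data capture. The SAP, which was not available here, can choose how to summarize, but it cannot recover site-level reactions that were never written down. Section 1.5 says the relationship between volume, flow rate and tolerability will inform the design of the delivery device, so the descriptive rates matter even without a formal test.

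**Working it through.** **The plan's own figure.** The protocol gives no expected reaction rate, no correlation between sites and no power statement for tolerability. Its only power figure (4.8.2) is for AUC: 84% for a 1.5-fold difference, CV 37%, 15 per cohort, two-sided 0.05. A two-sample t-test on the log scale, with SD √ln(1 + 0.37²) = 0.358, gives 84.9%, so that figure reproduces. This point does not depend on it.

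**Inputs.** From the protocol: the worst-of-two rule for Cohort 1, one site in Cohorts 2-4, and 15 subjects per cohort. Assumed and shown as a range: p, the probability that a single 1 mL site reacts (taken as equal for both sites); φ, the within-subject correlation between the two sites' yes/no outcomes; and q, the 2 mL reaction rate.

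**Formula.** The probability that at least one of two sites reacts is

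2p − [p² + φ·p(1 − p)].

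Subtracting p gives the excess over the per-injection rate:

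p(1 − p)(1 − φ).

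This is positive for every p strictly between 0 and 1 unless φ = 1, when the sites always agree. The direction is therefore fixed and the size is not.

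**Recorded Cohort 1 rate.**

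| Per-site rate p | φ = 0 | φ = 0.5 | φ = 1 |
|---|---|---|---|
| 0.10 | 0.19 | 0.145 | 0.10 |
| 0.20 | 0.36 | 0.28 | 0.20 |
| 0.30 | 0.51 | 0.405 | 0.30 |

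For example, at p = 0.20 the excess is 0.20 × 0.80 = 0.16 when φ = 0 and 0.08 when φ = 0.5. Over these values of p, the rate rises by 9 to 21 percentage points if sites are independent, by 4.5 to 10.5 points at φ = 0.5, and by nothing at full agreement.

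**Effect on the volume comparison.** The difference seen is q − p − p(1 − p)(1 − φ). With p = 0.20 and q = 0.40, the per-injection difference of 20 points appears as:
- 0.40 − 0.36 = 4 points if sites are independent;
- 0.40 − 0.28 = 12 points at φ = 0.5;
- 20 points at full agreement.

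It vanishes only in special cases, such as independent sites with q exactly 0.36.

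**What 15 per cohort could show.** Two-sided Fisher exact test at 0.05, treating each cohort as 15 single observations:
- 0.20 versus 0.40: power is 11% if Cohort 1 is recorded at its per-site rate, 4% at φ = 0.5 and 2% at φ = 0.
- 0.20 versus 0.50: 25%, 12% and 5%.

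Power is low throughout, so the scoring rule is not the only limit.

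**Pain and pruritus.** The same calculation cannot be made. If subjects report the worse site, the score is shifted up relative to one site. If they average, it need not be. If they add, it is shifted up further. The text does not say which.

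**The case against.** A reader might infer that the reference arm is inflated in every tolerability comparison and that a volume effect is hidden. The documents do not support that, for these reasons:

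- **Two questions are stated.** For the regimen comparison in 1.5 and 3.2.3, the burden of both injections on the subject is the right quantity, and the worst site is a reasonable summary of it. The rate is not inflated for that purpose.
- **Flow rate is untouched.** Hypothesis 2 can be examined across Cohorts 2-4, all with one 2 mL injection and one site.
- **The size is assumed.** Under 4.5.1.5 the two sites are on the same side of the abdomen, in the same subject, with injections given concurrently. Independence is therefore likely to be the upper end of the inflation.
- **The combined VAS is not a stated maximum.** What is missing there is a combining rule. With sites possibly only 3 cm apart, subjects may also find separate scores hard to give.
- **Hypothesis 1 has other limits.** It is posed at a given flow rate, and no 2 mL cohort runs at 6 mL/min. Cohorts 3-4 use a different insertion set (4.5.1.5). The assessor cannot be blinded to Cohort 1 (4.6.2).
- **The analysis is descriptive,** in a study that calls itself exploratory.

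All of this stands as a limit on the claim. It does not remove the core. For reactions under Hypothesis 1 the shift has a known direction, a descriptive rate carries it just as a test would, and the other limits are no reason to add an avoidable one.

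The Appendix 2 questionnaire was not in the text reviewed, so per-site fields on the form cannot be ruled out. Section 4.3.3.4 nevertheless asks for one overall record.

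**Conclusion.** The point holds for local injection-site reactions under secondary Hypothesis 1. The rule raises the recorded Cohort 1 rate above the per-injection rate unless the two sites always agree, and so attenuates a volume effect. The amount cannot be determined from the protocol: it depends on a per-site rate and a between-site correlation that are not given, and at full agreement it is zero.

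It does not extend to the regimen comparison or to the flow-rate comparison among Cohorts 2-4. For pain and pruritus, only the undefined combining rule can be criticized. Saying that the effect is hidden goes too far, because it disappears only for particular combinations of rates and correlation. This is an inexpensive improvement to a secondary, descriptive endpoint. It has to be made before dosing, because the site-level information cannot be recovered afterwards.

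**What to change.** In 4.3.3.4, complete the Appendix 2 questionnaire separately for each Cohort 1 site (A and B) at every time point. Then report two summaries:
- per injection, allowing for two sites per subject, for Hypothesis 1;
- per subject, as the worst of two derived from the site records, for comparing 2×1 mL with 1×2 mL.

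In 4.3.3.2 and 4.3.3.3, keep the overall VAS as a regimen-level measure and state how subjects should combine the two sites. Add a per-site VAS where subjects can tell the sites apart.

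The cost is one extra questionnaire at each of 10 scheduled time points in 15 subjects (10 × 15 = 150 forms), plus any per-site VAS. No extra visits or staff are needed, and Cohort 1 assessments become slightly longer. The change does not cure the other limits on Hypothesis 1 (unmatched flow rate, differing insertion sets, unblinded assessment of Cohort 1), which should be stated when the result is reported.
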